6.4. Appendix 4 Protocol Deviations

Major protocol deviations and major protocol deviations potentially impacting immunogenicity (see Section 5.1.3) will be summarized. The list of major protocol deviations with their coded terms to be excluded from the immunogenicity analyses will be specified in the Major Protocol Deviation Criteria document.

In general, the following list of major protocol deviations may have the potential to impact participants' rights, safety or well-being, or the integrity and/or result of the clinical study. Participants with major protocol deviations will be identified prior to database lock and the participants with major protocol deviations will be summarized by category. The different Protocol Deviation categories are:

- Developed withdrawal criteria but not withdrawn
- Entered to the study but did not satisfy eligibility criteria
- Received a disallowed concomitant treatment
- Received wrong treatment or incorrect dose
- Other

Participants or samples may be excluded from PPI-A or PPI-NVN based on the protocol deviations developed during the study.

6.5. Appendix 5 Prior and Concomitant Medications

Prior and Concomitant medications will be coded using the World Health Organization Drug Dictionary (WHO-DD).

Prior medications are defined as any therapy used before the day of first dose (partial or complete) of study intervention. Concomitant medications are defined as any therapy used on or after the same day as the first dose of study intervention, including those that started before and continue on after the first dose of study intervention.

For all participants, concomitant therapies associated with an SAE, a suspected AESI, MAAEs, AEs leading to discontinuation will be recorded in the eCRF. The proportion of participants with concomitant medication associated with these events will be tabulated.

For all participants, concomitant therapies associated with COVID-19 infection will be captured in the electronic eCRF for the duration of the study. Duration of the study is from the first dose date till end of study (date of last visit PP366) or trial discontinuation, whichever occurs first. The proportion of participants with new concomitant medication associated with these cases will be tabulated. New concomitant medications are defined as medications not available at baseline or medication with an increased dosage (See below, New Concomitant Medications, for details), compared to baseline. Baseline medications are all medications reported prior to and at the day of first vaccination. In case a baseline medication is reported multiple times then only the last available record reported prior to or at the day of first vaccination will be used.

Concomitant therapies associated with unsolicited AEs will be collected, recorded in the eCRF from the time of first and second vaccination through 28 days after post-dose 1 or post-booster and the proportion of participants with concomitant medication will be tabulated. Concomitant therapies associated with solicited AEs will be collected by the participants, recorded in the eCRF from the time of first or second vaccination through 7 days after post-dose 1 or post-booster and the proportion of participants with concomitant medication will be tabulated.

Based on their start and stop date, concomitant therapies will be reported in each applicable phase.

If a concomitant therapy record is missing components of its start and/or stop dates (time, day and/or month and/or year):

In case of partial start or stop dates, the concomitant therapy records will be allocated to periods using the available partial information, without imputations. If, for example, only month and year are available, these will be compared to the month and the year of the periods, and the concomitant therapy record will be allocated to the period(s) where these date parts match. This rule may lead to assignment to multiple periods. In case it is clear the medication was taken after vaccination, the start will be allocated to the correct phase without the use of the start dates (time, day and/or month and/or year). In case of a completely missing end date, the concomitant therapy will be considered as ongoing at the end of the trial.

There will be special attention to any systemic use of analgesics/antipyretics, started during 8 days following each vaccination (00:00 of day of vaccination + 7 days). Following CMCLASCD (ATC/DD codes) will be used for this: N02A (OPIOIDS) and N02B (OTHER ANALGESICS AND ANTIPYRETICS), M01A (ANTIINFLAMMATORY AND ANTIRHEUMATIC PRODUCTS, NON-STEROIDS) and M01B (ANTIINFLAMMATORY/ANTIRHEUMATIC AGENTS IN COMBINATION). The classes will be added in a footnote in all related tables and listings. For the use of analgesics/antipyretics which are taken on the day of vaccination an exception is made in case the time is before vaccination. In this case the concomitant medication is also allocated to the post-dose period.

Additionally, safety data listing will be presented for participants that uses corticosteroids.

Summaries of concomitant medications will be presented by ATC term and study phase. The proportion of participants who receive each concomitant medication will be summarized as well as the proportion of participants who receive at least 1 concomitant medication.

Prior medications will be summarized by ATC term. A Listing of Participants with Anti-D (rh) Immunoglobulins (J06BB01) will be provided.

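### Baseline medication for the COVID-19 treatment table need not be ongoing at first vaccination, so a drug restarted at the same or a lower dose is not counted as new

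*SAP*

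**What the plan says.** All the relevant text is in SAP Section 6.5 (Appendix 5, Prior and Concomitant Medications).

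- The output: "The proportion of participants with new concomitant medication associated with these cases will be tabulated". The cases are participants with COVID-19, whose therapies are captured from first dose to the end of the study.
- The definition of new, relative to baseline: "New concomitant medications are defined as medications not available at baseline or medication with an increased dosage". A pointer follows: "See below, New Concomitant Medications, for details". No part of that name appears in the rest of the section.
- The comparator: "Baseline medications are all medications reported prior to and at the day of first vaccination".
- Repeated records of one drug: "only the last available record reported prior to or at the day of first vaccination will be used".
- A separate term used for the prior-medication summary: "Prior medications are defined as any therapy used before the day of first dose (partial or complete) of study intervention". It includes therapy already stopped.
- Dates are used for a different purpose: "Based on their start and stop date, concomitant therapies will be reported in each applicable phase". They play no stated part in deciding baseline status.

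**The concern.** The table should show how many women started or stepped up treatment because of COVID-19. For that, the comparator should be what a woman was taking when she was vaccinated. As written, it is what had been recorded for her up to and including that day, whether or not she was still taking it.

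Two kinds of record get into the baseline set that should not be there. One is a drug used and stopped before Day 1. The other is a drug first taken on Day 1 after the injection, for example for a reaction to the vaccine. Section 6.5 collects therapies for solicited events from the time of vaccination, so records of the second kind are actively sought. Because the comparator stays fixed at first vaccination while COVID-19 therapies are captured until about a year after delivery, an old record can block new status for a long time.

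What is at stake is one descriptive proportion, which can come out too low without any sign of it in the output.

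**Working it through.** The plan gives no figure to reproduce. The check applies the Section 6.5 rule literally, drug by drug.

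| History up to and including Day 1 | Use for COVID-19 | Baseline as written? | New as written? | Fresh start or increase since vaccination? |
|---|---|---|---|---|
| No record | Started | No | Yes | Yes |
| Ongoing | Same dose | Yes | No | No |
| Ongoing | Higher dose | Yes | Yes | Yes |
| Stopped before Day 1 | Restarted, same or lower dose | Yes | **No** | **Yes** |
| Stopped before Day 1 | Restarted, higher dose | Yes | Yes | Yes |
| First taken on Day 1 after the injection, then stopped | Restarted, same or lower dose | Yes | **No** | **Yes** |
| First taken on Day 1 after the injection, then stopped | Restarted, higher dose | Yes | Yes | Yes |

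The rule and the purpose of the table disagree in two rows, and in both the rule fails to count a fresh start. In no row does it count something that should not be counted, so the error has one direction.

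From drugs to participants: let T be the number of women with at least one COVID-19 drug that was started, restarted or increased since vaccination. Let M be those among them for whom every COVID-19 drug has a record up to Day 1, with the last such record at the same or a higher dose. Then

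tabulated count = T − M, with 0 ≤ M ≤ T.

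One drug without such a record, or one at a raised dose, keeps a woman in the count. The SAP has no data on medication use, so M cannot be placed within its limits.

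The Day 1 part can be set beside two other rules in the SAP:

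- Section 5.1 takes the baseline value from the last assessment before the first vaccination on Day 1. The medication rule takes in the whole day, including the hours after the injection.
- Section 6.5 gives special attention to systemic analgesics and antipyretics started from 00:00 on the vaccination day onward, and treats them as post-dose. An antipyretic taken after the injection is thus post-vaccination treatment in one output and a baseline medication in another.

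**The case against.** **The wording could mean ongoing use.** Read strictly, the comparator sentence could require a drug to be present both before and on Day 1, and the word *available* in the definition of new leans the same way. But the next sentence, on repeated records, accepts a record from before the day or on it. That makes one earlier record enough. Some ambiguity remains, and it is itself a reason to reword.

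**The text is incomplete rather than wrong.** The section points to further details that are not there, and Section 1 leaves output detail to the Data Presentation Specifications. This stands in part: the dead reference is a defect of its own. The pointer sits beside the dosage criterion, however, so the missing text may never have dealt with ongoing use. The comparator itself is stated in full.

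**The look-back is a protocol matter.** This stands. How far back prior medication is collected is not shown, and a short window would leave few stopped drugs in the baseline set. That limits how often the first kind of record arises. It does not touch Day 1 records.

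**The consequences are small.** This also stands. Section 2 states that no hypothesis is tested, COVID-19 occurrence is an exploratory endpoint, and a restarted drug still appears in the Section 6.5 summaries by ATC term and study phase. Those summaries are not specific to COVID-19, so they do not replace the table.

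**Conclusion.** The point holds, as a minor one. Applied as written, Section 6.5 does not count as new a drug that was stopped before Day 1, or first taken after the injection on Day 1, and then restarted for COVID-19 at the same or a lower dose. The tabulated proportion can be too low and cannot be too high. The conclusion rests on reading the comparator together with the sentence on repeated records, and on no narrowing text existing elsewhere.

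A reader might infer more than the SAP supports:

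- *That every restart is missed.* It is not; the dosage criterion catches a restart at a dose above the last baseline record.
- *That a large share of treated women drop out of the table.* The SAP has no figure from which a share could be derived, and one other new drug keeps a woman in.
- *That need for treatment is understated across the study.* One descriptive table is affected, and no primary endpoint is.
- *That new should be judged against medication in use just before the COVID-19 episode.* That is a different choice of reference, which would make any baseline definition redundant for this table. It is not a correction of this error.

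**What to change.** In Section 6.5, define baseline medications as those started before the first vaccination and still ongoing at the time of that vaccination. State that drugs stopped earlier, or started after the injection on Day 1, are not baseline, so that a later start or restart counts as new. Keep the last-record rule only to set the comparator dose of an ongoing drug. Supply the *New Concomitant Medications* details or delete the reference.

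This brings post-injection drugs on Day 1 into line with the baseline definition in Section 5.1 and with the post-dose handling of analgesics and antipyretics in Section 6.5. The exception in Section 6.5 that also allocates analgesics taken earlier on the vaccination day to the post-dose period is a phase rule and can stay as it is.

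The cost is a sentence or two and a small change in programming. Start and stop dates are already used to allocate therapies to phases, so no new data are needed. One limitation remains: Section 6.5 treats a therapy with a completely missing end date as ongoing at the end of the trial, so a stopped drug with no recorded end date would still be baseline if it was started before vaccination. A footnote to the table would cover this.

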6.6. Appendix 6 FDA Toxicity Grading Scale for Vaccine Trials

Adapted from the FDA Guidance document "Toxicity Grading Scale for Healthy Adult and Adolescent Volunteers Enrolled in Preventive Vaccine Clinical Trials" (September 2007)

Local Reaction to Injectable Product	Mild (Grade 1)	Moderate (Grade 2)	Severe (Grade 3)	Potentially Life Threatening (Grade 4)
Pain/Tenderness [#]	Aware of symptoms but easily tolerated; Does not interfere with activity; Discomfort only to touch	Notable symptoms; Requires modification in activity or use of medications; Discomfort with movement	Incapacitating symptoms; Inability to do work, school, or usual activities; Use of narcotic pain reliever	Hospitalization; Pain/tenderness causing inability to perform basic self- care function
Erythema [#]	25 – 50 mm	51 – 100 mm	>100 mm	Hospitalization; Necrosis or exfoliative dermatitis
Swelling [#]	25 – 50 mm	51 – 100 mm	>100 mm	Hospitalization; Necrosis

A: Tables for Clinical Abnormalities

[#] Revised by the sponsor.

Vital Signs *	Mild (Grade 1)	Moderate (Grade 2)	Severe (Grade 3)	Potentially Life Threatening (Grade 4)
Fever (°C) ** (°F)**	38.0 - 38.4 100.4 - 101.1	38.5 - 38.9 101.2 - 102.0	39.0 - 40.0 102.1 - 104.0	>40 >104.0
Tachycardia - beats per minute	101 – 115	116 – 130	>130	Hospitalization for arrhythmia [#]
Bradycardia - beats per minute***	50 - 54	45 – 49	<45	Hospitalization for arrhythmia [#]
Hypertension (systolic) - mm Hg	141 – 150	151 – 155	>155	Hospitalization for malignant hypertension [#]
Hypertension (diastolic) - mm Hg	91 – 95	96 – 100	>100	Hospitalization for malignant hypertension [#]
Hypotension (systolic) – mm Hg	85 - 89	80 - 84	<80	Hospitalization for hypotensive shock [#]
Respiratory Rate – breaths per minute	17 – 20	21 – 25	>25	Intubation

* Participant should be at rest for all vital sign measurements.

** For oral temperature: no recent hot or cold beverages or smoking.

*** When resting heart rate is between 60 – 100 beats per minute. Use clinical judgement when characterizing bradycardia among some healthy participant populations, for example, conditioned athletes.

[#] Revised by the sponsor.

Systemic (General)	Mild (Grade 1)	Moderate (Grade 2)	oderate (Grade 2) Severe (Grade 3)	
Vomiting [#]	No interference with activity or 1 – 2 episodes/24 hours	Some interference with activity or >2 episodes/24 hours	Prevents daily activity, requires outpatient IV hydration	Hospitalization; Hypotensive shock
Nausea [#]	Minimal symptoms; causes minimal or no interference with work, school, or self- care activities	Notable symptoms; Requires modification in activity or use of medications; Does NOT result in loss of work, school, or cancellation of social activities	IncapacitatingIncapacitatingactivity or use ofsymptoms;activity or use ofRequires bed restactivity or use ofand/or results in lossboes NOT result inof work, school, orcancellation ofactivities	
Diarrhea [#]	2 – 3 loose stools or <400 gms/24 hours	4 – 5 stools or 400 – 800 gms/24 hours	- 5 stools or 00 - 800 gms/24 ours 6 or more watery stools or >800 gms/24 hours or oral rehydration necessary	
Headache [#]	Minimal symptoms; causes minimal or no interference with work, school, or self- care activities	Notable symptoms; Requires modification in activity or use of medications; Does NOT result in loss of work, school, or cancellation of social activities	Incapacitating symptoms; Requires bed rest and/or results in loss of work, school, or cancellation of social activities; Use of narcotic pain reliever	Hospitalization; Inability to perform basic self-care functions
Fatigue [#]	Minimal symptoms; causes minimal or no interference with work, school, or self- care activities	Notable symptoms; Requires modification in activity or use of medications; Does NOT result in loss of work, school, or cancellation of social activities	Incapacitating symptoms; Requires bed rest and/or results in loss of work, school, or cancellation of social activities; Use of narcotic pain reliever	Hospitalization; Inability to perform basic self-care functions
Myalgia [#]	Minimal symptoms; causes minimal or no interference with work, school, or self- care activities	Notable symptoms; Requires modification in activity or use of medications; Does NOT result in loss of work, school, or cancellation of social activities	Incapacitating symptoms; Requires bed rest and/or results in loss of work, school, or cancellation of social activities; Use of narcotic pain reliever	Hospitalization; Inability to perform basic self-care functions

[#] Revised by the sponsor.

Systemic Illness	Mild (Grade 1)	Moderate (Grade 2)	Severe (Grade 3)	Potentially Life Threatening (Grade 4)
Illness or clinical adverse event (as defined according to applicable regulations)	No interference with activity	Some interference with activity not requiring medical intervention	Prevents daily activity and requires medical intervention	Hospitalization [#]

[#] Revised by the sponsor

B: Tables for Laboratory Abnormalities

Laboratory tests may be performed during routine medical care and assessment of AEs or other medical events based on the investigator's judgment.

The laboratory values provided in the tables below serve as guidelines and are dependent upon institutional normal parameters. Institutional normal reference ranges should be provided to demonstrate that they are appropriate.

Serum *	Mild (Grade 1)	Moderate (Grade 2)	Severe (Grade 3)	Potentially Life Threatening (Grade 4)**
Sodium – Hyponatremia mEq/L	132 - 134	130 - 131	125 - 129	< 125
Sodium – Hypernatremia mEq/L	144 - 145	146 - 147	148 - 150	> 150
Potassium – Hyperkalemia mEq/L	5.1 - 5.2	5.3 - 5.4	5.5 - 5.6	> 5.6
Potassium – Hypokalemia mEq/L	3.5 - 3.6	3.3 - 3.4	3.1 - 3.2	< 3.1
Glucose – Hypoglycemia mg/dL	65 - 69	55 - 64	45 - 54	< 45
Glucose – Hyperglycemia Fasting mg/dL Random – mg/dL	$100 - 110 \\ 110 - 125$	$111 - 125 \\ 126 - 200$	>125 >200	Insulin requirements or hyperosmolar coma
Blood Urea Nitrogen (BUN) mg/dL	23 – 26	27 – 31	> 31	Requires dialysis
Creatinine – mg/dL	1.5 – 1.7	1.8 - 2.0	2.1 – 2.5	> 2.5 or requires dialysis
Calcium – hypocalcemia mg/dL	8.0 - 8.4	7.5 - 7.9	7.0 - 7.4	< 7.0
Calcium – hypercalcemia mg/dL	10.5 - 11.0	11.1 - 11.5	11.6 - 12.0	> 12.0
Magnesium – hypomagnesemia mg/dL	1.3 - 1.5	1.1 - 1.2	0.9 - 1.0	< 0.9
Phosphorous – hypophosphatemia mg/dL	2.3 - 2.5	2.0 - 2.2	1.6 - 1.9	< 1.6
Creatine phosphokinase (CPK) – mg/dL	1.25 – 1.5 x ULN***	1.6 – 3.0 x ULN	3.1 –10 x ULN	> 10 x ULN
Albumin – Hypoalbuminemia g/dL	2.8 - 3.1	2.5 - 2.7	< 2.5	
Total Protein – Hypoproteinemia g/dL	5.5 - 6.0	5.0 - 5.4	< 5.0	
Alkaline phosphate – increase by factor	1.1 – 2.0 x ULN	2.1 – 3.0 x ULN	3.1 – 10 x ULN	> 10 x ULN
Liver Function Tests: alanine aminotransferase (ALT), aspartate aminotransferase (AST) - increase by factor	1.1 – 2.5 x ULN	2.6 – 5.0 x ULN	5.1 – 10 x ULN	> 10 x ULN

Serum *	Mild (Grade 1)	Moderate (Grade 2)	Severe (Grade 3)	Potentially Life Threatening (Grade 4)**
Bilirubin – when accompanied by any increase in Liver Function Test increase by factor	1.1 – 1.25 x ULN	1.26 – 1.5 x ULN	1.51 – 1.75 x ULN	> 1.75 x ULN
Bilirubin – when Liver Function Test is normal; increase by factor	1.1 – 1.5 x ULN	1.6 – 2.0 x ULN	2.0 – 3.0 x ULN	> 3.0 x ULN
Cholesterol	201 - 210	211 - 225	> 226	
Pancreatic enzymes – amylase, lipase	1.1 – 1.5 x ULN	1.6 – 2.0 x ULN	2.1 – 5.0 x ULN	> 5.0 x ULN

* The laboratory values provided in the tables serve as guidelines and are dependent upon institutional normal parameters. Institutional normal reference ranges should be provided to demonstrate that they are appropriate.

** The clinical signs or symptoms associated with laboratory abnormalities might result in characterization of the laboratory abnormalities as potentially life-threatening (Grade 4). For example, a low sodium value that falls within a Grade 3 parameter (125-129 mEq/L) should be recorded as a Grade 4 hyponatremia event if the participant had a new seizure associated with the low sodium value.

***ULN is the upper limit of the normal range.

Hematology *	Mild (Grade 1)	Moderate (Grade 2)	Severe (Grade 3)	Potentially Life Threatening (Grade 4)
Hemoglobin (Female) - mg/dL	11.0 - 12.0	9.5 - 10.9	8.0 - 9.4	< 8.0
Hemoglobin (Female) change from baseline value - mg/dL	Any decrease – 1.5	1.6 - 2.0	2.1 - 5.0	> 5.0
Hemoglobin (Male) - mg/dL	12.5 - 13.5	10.5 - 12.4	8.5 - 10.4	< 8.5
Hemoglobin (Male) change from baseline value – mg/dL	Any decrease – 1.5	1.6 - 2.0	2.1 - 5.0	> 5.0
WBC Increase - cell/mm ³	10,800 - 15,000	15,001 - 20,000	20,001 - 25,000	> 25,000
WBC Decrease - cell/mm ³	2,500 - 3,500	1,500 - 2,499	1,000 - 1,499	< 1,000
Lymphocytes Decrease - cell/mm ³	750 - 1,000	500 - 749	250 - 499	< 250
Neutrophils Decrease - cell/mm ³	1,500 - 2,000	1,000 - 1,499	500 - 999	< 500
Eosinophils - cell/mm ³	650 - 1500	1501 - 5000	> 5000	Hypereosinophilic
Platelets Decreased - cell/mm ³	125,000 - 140,000	100,000 – 124,000	25,000 - 99,000	< 25,000
Prothrombin time (PT) – increase by factor	1.0 – 1.10 x ULN**	1.11 – 1.20 x ULN	1.21 – 1.25 x ULN	> 1.25 ULN
Partial thromboplastin time (PTT) – increase by factor	1.0 – 1.2 x ULN	1.21 – 1.4 x ULN	1.41 – 1.5 x ULN	> 1.5 x ULN
Fibrinogen increase - mg/dL	400 - 500	501 - 600	> 600	
Fibrinogen decrease - mg/dL	150 - 200	125 – 149	100 – 124	< 100 or associated with gross bleeding or disseminated intravascular coagulation (DIC)

* The laboratory values provided in the tables serve as guidelines and are dependent upon institutional normal parameters. Institutional normal reference ranges should be provided to demonstrate that they are appropriate.

** ULN is the upper limit of the normal range.

VAC31518 (JNJ-78436735)

Statistical Analysis Plan VAC31518COV2004 HORIZON 1

Urine *	Mild (Grade 1)	Moderate (Grade 2)	Severe (Grade 3)	Potentially Life = Threatening (Grade 4)
Protein	Trace	1+	2+	Hospitalization or dialysis
Glucose	Trace	1+	2+	Hospitalization for hyperglycemia
Blood (microscopic) – red blood cells per high power field (rbc/hpf)	1 - 10	11-50	> 50 and/or gross blood	Hospitalization or packed red blood cells (PRBC) transfusion

* The laboratory values provided in the tables serve as guidelines and are dependent upon institutional normal parameters. Institutional normal reference ranges should be provided to demonstrate that they are appropriate.

